Alectinib is a second-generation kinase inhibitor indicated for the treatment of patients with ALK+ metastatic NSCLC. Alectinib was first FDA approved in December 2015 for the treatment of ALK+ NSCLC in patients following treatment with the first generation ALK inhibitor crizotinib. In November of 2017, the FDA approved alectinib for use as first-line treatment for ALK+ metastatic NSCLC.

The approval was based on the Phase 3 ALEX trial of 303 first-line ALK+ NSCLC patients. Treatment with alectinib demonstrated a significantly reduced risk of progression or death by 47 percent (HR=0.53, 95 percent CI: 0.38, 0.73, p<0.0001) compared to crizotinib. Median

PFS was 25.7 months (95 percent CI: 19.9, not estimable) for patients treated with alectinib compared with 10.4 months (95 percent CI: 7.7, 14.6) for patients who received crizotinib. Treatment with alectinib also reduced the risk of the brain or central nervous system (CNS) metastasis compared to crizotinib by 84 percent (HR=0.16, 95 percent CI: 0.10, 0.28, p<0.0001).[1]

Likewise, ceritinib (Zykadia®), has been tested in the frontline setting. In the ASCEND-4 Phase 3 trial, ceritinib was compared to a platinum/pemetrexed demonstrating a median progression free survival of 16.6 months as compared to only 8.1 months in the platinum/pemetrexed chemotherapy arm. Other comparisons of second and third generation ALK inhibitors to ceritinib are ongoing.[16]

More recently, in November 2018, the FDA granted accelerated approval to lorlatinib for patients with ALK+ metastatic NSCLC whose disease has progressed on crizotinib and at least one other ALK inhibitor or whose disease has progressed on alectinib or ceritinib as the first ALK inhibitor therapy.[17] The accelerated FDA approval was converted to a full approval and the indication was expanded to include first-line treatment for patients with ALK+ metastatic NSCLC in March 2021. [18]

With the availability of several therapeutic agents, current treatment patterns and outcomes with use of multiple ALK-inhibitor treatments in sequence are not well understood. For patients with ALK positive NSCLC, first-line therapy with alectinib is the preferred treatment option, however, sequence of therapy is not well-defined. This study aims to understand patient profiles, treatment patterns, and clinical outcomes among ALK+ NSCLC patients treated with alectinib, and post-alectinib treatment patterns and outcomes.

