9.3. Setting

The study population will consist of patients with a diagnosis of NSCLC receiving alectinib within The US Oncology Network and Non-Network sites. The US Oncology Network includes approximately 1,400 affiliated physicians operating in over 480 sites of care across states and treats approximately 1.2 million US cancer patients annually. There are more than 2,650 active Non-Network supported oncology and non-oncology sites of care. [19]

Figure 1 and Figure 2 presents graphical depictions of the study time periods, which are as follows:

- Phase 1 and 2 study observation period: 01 June 2017 31 December 2019.
- Phase 1 and 2 study identification period: 01 June 2017 30 June 2019.
- Phase 3 study refresh observation period: 01 June 2017 31 August 2021.
- Phase 3 study refresh identification period: 01 June 2017 31 August 2020.
- Phase 3 exploratory analysis study observation period: 02 November 2018 31 August 2021.
- Phase 3 exploratory analysis study identification period: 02 November 2018 31 August 2020.
- Phase 1 and 2 index date-1: start date of alectinib treatment during the study identification period
- Phase 1 and 2 index date-2: start date of the subsequent treatment following alectinib, among patients who receive the next treatment during the study observation period
- Phase 3 study refresh index date-1: start date of alectinib treatment during the study identification period
- Phase 3 study refresh index date-2: start date of the subsequent treatment following alectinib, among patients who receive the next treatment during the study observation period
- Phase 3 exploratory analysis index date-1: start date of lorlatinib treatment during the study identification period
- Phase 3 exploratory analysis index date-2: start date of lorlatinib treatment among patients who receive next treatment during the study observation period
- Baseline: The baseline period or "at index" includes up to 30 days prior to and up to 30 days after index. If a patient has multiple baseline values for a particular demographic or clinical characteristic during this ± 30-day time frame, the one closest (in absolute value) prior to the index date will be used. If no values prior to index are available, then the one closest to the index date up to 30 days after will be used.

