- Prior medical history: Patients' available history in the iKnowMed (iKM) EHR will vary based on the length of disease and the time within The US Oncology Network. Disease characteristics such as time of NSCLC diagnosis and date of metastatic

disease will take into account patients' available medical history. The prior medical history period will end the day prior to the index date-1.

• Follow-up: Patients will be followed through the end of the study observation period, date of last visit or date of death, whichever occurs first. For analysis, patients will have a potential of at least 6 months of follow-up duration; however, patients will have variable follow-up time periods, depending on their index dates and last contact dates.

9.3.1. Phase 1 and 2 (original study) and Phase 3 (refresh study) population Inclusion criteria

Patients must meet all of the following inclusion criteria to be eligible for inclusion in the study:

- 1. Patients with a documented diagnosis of NSCLC.
- 2. Patients \geq 18 years of age at initial recorded diagnosis of NSCLC.
- 3. Patients who received treatment with alectinib within The US Oncology Network or Non-Network sites during the study identification period.
- 4. During the study observation period, patients observed with at least 2 visits⁴ after the index date-1.

Exclusion criteria

Patients meeting any of the following criteria will not be included in the study:

- 1. Receipt of treatment indicated for another primary cancer or diagnosis of another primary cancer (with the exception of non-melanotic skin cancer), within 5 years of index date-1 will be excluded.
- 2. Patients enrolled in clinical trials prior to receiving alectinib during the study ID period (index date-1), will be excluded.

⁴ Visits are defined as physical encounters with the practice, detected by vital sign records. The second and third visits must be observed after the index date-1 to demonstrate continuity of care. There is no required time span between the additional visits and the index date-1.

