Reason for ALK inhibitor (alectinib, and subsequent treatment) treatment discontinuation	Chart review	Treatment characteristics	Study observation period	Data for alectinib and subsequent treatment discontinuation reason will exclusively come from chart review. Reviewers will be asked to select reason(s) as explicitly documented in patients' charts. If available, reason patients discontinued treatment will be abstracted: Completion of therapy Provider-documented disease progression Death Insurance/cost-related Loss to follow-up Patient preference Toxicity Other No information Reviewers will specify other reasons; these will be reported if any represent >5% of patients.	
ALK inhibitor treatment sequencing	iKM structured data + chart review	Treatment pattern	Study observation period	ALK inhibitor treatment paths (e.g. initiate crizotinib followed by ceritinib, initiate crizotinib followed by alectinib, etc.)	
Front-line alectinib	iKM structured data + chart review	Treatment pattern	Study observation period	First treatment administration of alectinib not preceded by any other product for NSCLC therapy except up to 3 months of chemotherapy and immunotherapy preceding alectinib therapy initiation to classify patient as receiving 1L alectinib	
Clinical outcomes					
Last US Oncology Network visit date	iKM structured data + chart review	Clinical outcomes	Study observation period	Each patient's most recent visit date, prior to or on close of study observation period, in the structured data will be recorded. A visit is defined as a physician encounter with the practice where either treatment is given, or vital signs are recorded. For patients with a death date, this last visit date should occur prior to the death date.	

Table 1. Study variables and operational definitions

Variable	Source(s)	Role(s) in study	Period of measurement	Operational definition
				This will not be reported separately; it will be used in calculating the patient's available follow-up time as a descriptive measure. Available follow-up time = Integer (latest of last visit date or death date – index date +1).7

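### Table 1 measures front-line status and ALK-inhibitor sequence over a period that opens on the first day of identification, in conflict with definitions that need the full pre-index treatment history

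*Combined protocol and SAP*

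**What the plan says.** Section 9.4, Table 1, assigns each variable a period of measurement. For front-line alectinib and for ALK-inhibitor treatment sequencing it is the study observation period. The row on NSCLC treatment before index is damaged in the available text; what survives of its period cell points the same way, but this cannot be confirmed.

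Section 9.3 fixes the windows: "Phase 1 and 2 study observation period: 01 June 2017 31 December 2019" beside "Phase 1 and 2 study identification period: 01 June 2017 30 June 2019". The refresh has "Phase 3 study refresh observation period: 01 June 2017 31 August 2021" and the lorlatinib analysis "Phase 3 exploratory analysis study observation period: 02 November 2018 31 August 2021"; their identification periods also open on the same day as observation.

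The operational definitions carry no calendar limit. Front-line is "First treatment administration of alectinib not preceded by any other product for NSCLC therapy", apart from up to three months of chemotherapy and immunotherapy. Sequencing covers "ALK inhibitor treatment paths (e.g. initiate crizotinib followed by ceritinib, initiate crizotinib followed by alectinib, etc", so it includes drugs given before alectinib.

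Section 9.3 also defines a prior medical history period with no start limit, ending the day before index date-1. Its examples are "Disease characteristics such as time of NSCLC diagnosis and date of metastatic" disease; treatment is not mentioned. Section 9.8 says no separate analysis plan will be written, and Section 9.8.2 refers to Table 1 for how derived variables are calculated.

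**The concern.** The period column and the definitions give different answers for early-index patients, and the plan does not say which governs. If the extraction follows the column, a patient who took crizotinib only before 01 June 2017 and started alectinib that summer has no visible earlier product and counts as front-line. These first months matter: Section 7 dates first-line approval of alectinib to November 2017, and before then the indication was after crizotinib. Short look-back therefore falls on the patients most likely to be pretreated.

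The lorlatinib analysis is the more exposed. Section 7 gives the November 2018 indication as patients "whose disease has progressed on crizotinib and at least one other ALK inhibitor", or whose disease progressed on alectinib or ceritinib as first ALK inhibitor. Early starters should therefore have a prior ALK inhibitor, yet a window opening on 02 November 2018 could hide it. This analysis uses structured data only, so chart review cannot restore what is lost. Any such loss would shrink with calendar time, so sequences compared across years could show a trend that is an artefact of the window.

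At stake are the sequencing part of Objective 11 and the front-line versus non-front-line strata in the structured analyses. The limitation in Section 9.10.1 concerns treatment before the first Network encounter or outside the Network, not records already in iKM that a date filter would exclude.

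**Working it through.** The plan states no look-back figure, so there is none to reproduce. The check sets the labels side by side and then does date arithmetic.

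**Are the labels deliberate?** The other-cancer row of Table 1 adds prior medical history to the observation period. The rows for initial diagnosis, stage and metastatic date use medical history prior to index. The table thus distinguishes history from observation elsewhere, and a programmer could reasonably take the narrower label at face value.

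**Look-back under that reading.** Look-back = index date − opening date of the observation period. For a patient indexed on the opening day it is 0 days.

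Assumption: index dates are spread evenly over the identification period. Then the share with look-back under m months = m × 30.4375 / D, where D is the inclusive length of the identification period (dates from Section 9.3) and 30.4375 is the days-per-month divisor in the plan's own duration-of-therapy formula (Section 9.8.3). The numerators are 91.3, 182.6 and 365.25 days for 3, 6 and 12 months.

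| Analysis | Identification period | D | <3 months | <6 months | <12 months |
|---|---|---|---|---|---|
| Phases 1/2 | 01 Jun 2017 to 30 Jun 2019 | 760 | 12% | 24% | 48% |
| Phase 3 refresh | 01 Jun 2017 to 31 Aug 2020 | 1188 | 8% | 15% | 31% |
| Lorlatinib | 02 Nov 2018 to 31 Aug 2020 | 669 | 14% | 27% | 55% |

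Applied to the 134 lorlatinib patients in Section 9.6, the shares give about 18, 37 and 73 patients. That feasibility count runs to 31 December 2020, four months past identification, so these numbers are indicative only.

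**From exposure to error.** An earlier drug is lost entirely only if its last record lies before the window opens. If that record precedes index by g months, the drug is missed when look-back is below g, so the same formula applies with g for m:

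- g = 0: 0% in every analysis.
- g = 1 month: 30.4375/760 = 4.0% in Phases 1/2; 30.4375/669 = 4.5% for lorlatinib.
- g = 3 months: 12% and 14%.

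For the immediately preceding drug, g is small if the switch is prompt and any in-window record counts. For a drug further back, such as crizotinib before alectinib before lorlatinib, g is at least the time on the intervening drug (assuming no overlap), so the 6- and 12-month columns become relevant. The documents give no distribution of g, so no misclassification rate follows.

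**The case against.** The best defence is that the definitions should govern. They have no calendar limit, and the three-month chemotherapy and immunotherapy exception cannot be fully applied to someone indexed in June to August 2017 without records from before the window, so the row itself presupposes such records. The prior medical history period is open-ended and its examples are only illustrative. This stands far enough to rule out the claim that the plan definitely cuts off earlier therapy. It does not resolve the conflict, because nothing in the plan gives the definition precedence over the period column.

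A reader might also infer more than the documents support:

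- **Chart selection and front-line PFS are corrupted.** Sections 9.3.4.1 and 9.3.4.2 verify eligibility during abstraction and allow up to 150 and 125 charts to reach 100 patients. Under Section 9.8.1 chart data supersede structured data in the final analysis, and progression dates come only from charts. A loose structured screen would mainly cost abstraction effort. The protection is partial: the same period label also covers chart-sourced data in these rows, and structured-only patients are not checked.
- **Objectives 2 and 6 are distorted.** They mainly concern treatment after alectinib, which look-back does not shorten.
- **Most lorlatinib patients are misclassified.** Treating the cited 25.7-month median PFS as exponential time on alectinib, exp(−ln 2 × t/25.7) gives 85%, 72% and 55% at t = 6, 12 and 21.9 months after the window opens. These are shares whose preceding drug started before the window. A drug that started earlier but has a record inside the window need not be lost, so they are not error rates.

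**Conclusion.** The concern holds as an unresolved conflict within Table 1 and Section 9.3. Read by its period column, the plan gives early-index patients little or no look-back for variables whose definitions need all earlier treatment. The direction of any resulting error is clear: pretreated patients move into the front-line stratum of the structured analysis, and lorlatinib sequences are shortened. The effect on abstracted samples is limited.

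The size is known only as exposure: about 14%, 27% and 55% of lorlatinib patients, and 12%, 24% and 48% of Phase 1/2 patients, with under 3, 6 and 12 months of look-back. This rests on evenly spread index dates and on the period column being applied literally. The documents support neither a misclassification rate nor the conclusion that the classifications are in fact wrong. The ambiguity should still be settled before extraction, because Table 1 is the only derivation specification.

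**What to change.** In Table 1, change the period of measurement for prior NSCLC treatment, ALK-inhibitor treatment sequencing and front-line alectinib to prior medical history plus study observation period, the combination already used in the other-cancer row. In the prior medical history paragraph of Section 9.3, name treatment history, and state that all available iKM treatment records before index date-1 (alectinib or lorlatinib) are searched with no calendar lower bound.

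This removes the truncation imposed by the calendar. Gaps from care outside the Network remain, as Section 9.10.1 acknowledges. The cost is two wording changes, a wider date filter at extraction, and a slightly smaller front-line pool if some patients are reclassified.

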9.3.3. Cohort definitions and stratifications

Separate study cohorts will be considered in all phases of the project.

For Phase 1, results will be presented for all patients who meet study eligibility criteria listed in Section 9.3.1 and stratified by subsequent treatment following alectinib (as described in Section 9.1).

For Phase 2, a sample of patients who received alectinib as front-line therapy (i.e., first treatment administration of alectinib not preceded by any other product for NSCLC therapy) will be selected for chart review and results will be presented for all patients selected for chart review and stratified by subsequent treatment following alectinib.

For Phase 3, the stratifications for Phases 1 and 2 will be replicated for all patients who meet study eligibility criteria with the extended identification and observation period as outlined in 9.3. An additional sample of patients identified for chart review for Phase 3 will be stratified by the specified subsequent treatment groups specified in 9.3.1.

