9.3.4.2. Chart review for Phase 3 study refresh

Two groups of patients are planned for chart review during Phase 3. The first group includes patients from Phase 2 chart review who had ongoing treatment at the end of the observation period (31 December 2019). These patients will undergo additional follow-up through 31 August 2021.

An additional sample of approximately 100 patients who meet the Phase 3 eligibility criteria and received alectinib as front-line therapy and received subsequent treatment among the following groups will undergo chart review:

- Alectinib → lorlatinib
- Alectinib → crizotinib
- Alectinib → brigatinib
- Alectinib only
- Alectinib \rightarrow chemotherapy (optional)

In the event the total number of eligible patients following structured data screening exceeds the planned number of charts for review, a random sample will be selected.

During the course of abstraction, patients' eligibility for the study will be verified and some of these patients may be found to be ineligible. A total of up to 125 charts are assumed to be reviewed to identify at least 100 patients who received post-alectinib treatment from the above listed priority groups.

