Date of metastatic disease diagnosis	iKM structured data + chart review	Baseline characteristic	Medical history prior to index	Date of first recorded diagnosis of metastatic disease within the EHR. Patients will be qualified initially based on the date identified in the structured data; this will be confirmed during chart review among patients selected for chart review. Ultimately, the primary source will be the chart if available. All patients receiving ALK inhibitors are assumed to be metastatic at time of ALK inhibitor treatment. Structured data will confirm the patient as metastatic and as available, indicate the earliest associated date of any of these criteria: 1) Stage IV disease 2) TNM with M value of 1 3) Record of location of metastatic disease 4) Current or prior disease status containing reference to metastatic disease
Metastatic disease at diagnosis	iKM structured data + chart review	Categorized as: Baseline characteristic	At diagnosis	Categorized as: Yes No No information Note, "no information" can indicate that metastases were not documented in the chart, not necessarily that patients did not have metastases.
Distant metastatic site(s) at index date-1 (alectinib or lorlatinib start date)	iKM structured data + chart review	Baseline characteristic	Baseline	Baseline metastatic location(s) will be identified and categorized as: Bone (single) Bone (multiple) Brain CNS Liver (single) Liver (multiple) Lung (single) Lung (single) Lung (pleural effusion) Lymph nodes (regional) Lymph nodes (distant) Ovary Other No information Note, "no information" can indicate that metastases were not documented in the chart, not necessarily that patients did not have metastases.

Table 1. Study variables and operational definitions

Variable	Source(s)	Role(s) in study	Period of measurement	Operational definition
Tumor histology	iKM structured data	Baseline characteristic	Baseline	Categorized as: Adenocarcinoma Squamous Large Not otherwise specified (NOS) Missing/unknown
ALK testing order source and date	iKM Chart Review	Baseline characteristic	Baseline	Categorized as: Lab report Order requisition Pathology report Progress note
ALK mutation status	iKM structured data + Chart Review	Baseline characteristic	Baseline	Categorized as: Not performed Positive fusion/rearrangement Negative Equivocal Indeterminate QNS Other Inconclusive Not documented If multiple test results are available, used last documented value

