9.8.1. Analysis sets

Phases 1 and 2

For analyses performed to meet the Phase 1 objectives, all patients who the meet the eligibility criteria defined in Section 9.3.1 will be considered. The study cohorts will be identified based on subsequent therapy following alectinib. For these analyses, datasets consisting of the structured data elements, plus the LADMF to confirm vitality status, required for the landscape analyses will be constructed.

The Phase 2 (chart review) analyses will be limited to a sample of 100 qualified front-line alectinib patient charts identified from Phase 1. The chart review analysis sets will be constructed from both structured and unstructured data, with the LADMF used to confirm vitality status.

Phase 3

For analyses performed to meet the Phase 3 unstructured objectives, all patients who the meet the eligibility criteria defined in Section 9.3.1 will be considered. The study cohorts will be identified based on subsequent therapy following alectinib. For these analyses, datasets consisting of the structured data elements, plus the LADMF to confirm vitality status, required for the landscape analyses will be constructed.

Phase 3 chart review analyses will include a subset of patients from Phase 2 chart review who had ongoing treatment at the end of the observation period and an additional sample of 100 qualified front-line alectinib patients from Phase 3. The chart review analysis sets will be constructed from both structured and unstructured data, with the LADMF used to confirm vitality status.

Some data elements will be captured with both structured and unstructured data. Since the chart review data are expected to provide a richer source of information, if data are available from both sources for a single patient, then chart review data will supersede what is available in the structured iKM data for the final analysis. To account for this, a final analysis data set will be constructed and used to update the landscape analyses once chart review data are available.

For Phase 3 exploratory analysis, all patients who meet the eligibility criteria defined in Section 9.3.2 will be considered. The study cohorts will be identified based on subsequent therapy following lorlatinib. For these analyses, datasets consisting of the structured data elements will be constructed.

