All descriptive tables will be presented for each of the study cohorts defined above and, as supported by the final sample size, stratified by front-line alectinib and non front-line alectinib treatment groups.

For Phase 3 exploratory objectives, descriptive analyses will be conducted to evaluate the demographic, clinical and treatment characteristics among patients treated with lorlatinib. Results will be reported in aggregate. Categorical variables (e.g., ECOG performance status) will be reported as frequency and percentage. Continuous variables such as age will be reported as mean, standard deviation, median and range (minimum-maximum). In the case of missing observations, the number and percentage of missing values will be reported.

Clinical outcomes

ALK inhibitor DOT, OS, PFS will be assessed using the Kaplan-Meier method with 95% CIs, and summary tables of the number of events and censored patients at 3, 6, 12, 18, and 24 months. Further details about these calculations are presented below and in Table 1.

Clinical outcome results will be presented by study cohort and stratified by front-line alectinib and non-front line alectinib (pending sample size).

Overall survival (OS) will be defined as the interval between start date of alectinib to the date of death as documented in the LADMF and/or iKM EHR database. Patients who did not die will be censored on the study end date or the last visit date available in the database, whichever occurred first. In order to handle censoring, the Kaplan-Meier method will be used to calculate median overall survival with 95% confidence intervals (in number of months). Additionally, 3, 6, 12, 18, and 24-month survival probabilities will be reported. OS will be estimated for the full study population and stratified by study cohort. Log-rank tests will be used to assess statistical differences.

Duration of Therapy (DOT) for ALK inhibitors: An intent to treat approach will be used. DOT will be defined as duration of time (in months) between alectinib treatment initiation and discontinuation, or the last administration date of alectinib, or start date of a subsequent ALK inhibitor, initiation of any subsequent non-ALK inhibitor treatment (as a proxy for evidence of discontinuation), death or check-in in a hospice will be used as a stop date.

There may be some patients who do not have evidence of discontinuation or who do not move on to a subsequent therapy.

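### Front-line alectinib has two incompatible definitions; the rules for picking an ALK result and the 30-day biomarker window also need repair, and the ALK+ proxy should be stated

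*Combined protocol and SAP*

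**What the plan says.** **Front-line.** Section 9.3.3, which sets the Phase 2 chart sample, defines front-line as "first treatment administration of alectinib not preceded by any other product for NSCLC therapy". The Abstract and Section 8 use the same strict definition. The Front-line alectinib row of Table 1 reads "not preceded by any other product for NSCLC therapy except up to 3 months of chemotherapy and immunotherapy preceding alectinib therapy initiation". Section 9.3.4.2 says that the new Phase 3 patients who "received alectinib as front-line therapy and received subsequent treatment among the following groups will undergo chart review", without saying which definition applies; Section 9.2 does the same. Section 9.8.1 analyzes carried-over Phase 2 charts together with "an additional sample of 100 qualified front-line alectinib patients from Phase 3". Section 9.8.3 stratifies clinical outcomes by front-line status if numbers allow, and gives that split as an example of a comparison at the 0.05 level.

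**ALK and other markers.** Table 1 gives ALK status, histology, BRAF, EGFR, PD-L1, ROS1 and MET the measurement period Baseline. Section 9.3 says that this period "includes up to 30 days prior to and up to 30 days after index" and that, among several values, "the one closest (in absolute value) prior to the index date will be used"; a later value is used only if none precedes index. The ALK status row has its own instruction: "If multiple test results are available, used last documented value".

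**The ALK+ label.** The Abstract and Section 8 describe the population as ALK+. Section 9.3.1 requires an NSCLC diagnosis, adult age, alectinib receipt and follow-up visits, but no positive ALK result. Section 9.6 reports an ALK result for 217 of 293 feasibility patients.

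**The concern.** Front-line status is both a gate to chart review and an analysis stratum. If it has two meanings, two analysts following the protocol can draw different chart samples and form different strata for DOT, OS and PFS. Section 9.8 says that no further analysis plan will be written, so no later document will choose between them.

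The ALK rules raise a similar problem on a smaller scale: the same record can give two different baseline ALK values. The window is a separate matter. Histology and molecular results are often obtained at diagnosis or before an earlier line, and a strict window around index would show them as missing.

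The label matters for interpretation. A reader of outcomes headed ALK+ should know that treatment, not a test, defined the group.

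**Working it through.** **(a) Front-line, definitions side by side.** Take a patient with two months of chemotherapy immediately before alectinib.
- Abstract, Section 8, Section 9.3.3: a prior NSCLC product exists, so not front-line.
- Table 1: the prior therapy falls within the 3-month exception, so front-line.

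Both cannot hold. The number of such patients is not given. For scale only, Section 9.6 puts about half of 293 in the front-line setting: 293/2 = 146.5. Assume that this count follows Table 1 and that 5% to 30% qualify only through the exception. The strict group is then 146.5 × 0.95 = 139 down to 146.5 × 0.70 = 103, and 100 charts become 95 down to 70. These figures only restate the assumed share.

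**(b) ALK selection, worked example.** Take results at day −20 and day +10, both inside the 30-day window.
- Section 9.3: closest before index, so day −20.
- ALK row: last documented, so day +10.

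Reading the ALK row as the last value within the window does not remove the conflict. The row's categories include QNS and inconclusive, so under the ALK row a failed later test would displace an earlier positive. The other marker rows have no rule of their own, so for them the only question is the width of the window.

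**Window, lorlatinib cohort.** Identification runs from 02 November 2018 to 31 August 2020 (Section 9.3). Section 7 describes the indication in that period as following progression on earlier ALK inhibitors; first-line use was added in March 2021. For such patients the original ALK test would usually predate lorlatinib by more than 30 days. This is an inference; the documents give no count.

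**(c) ALK results.**
- Reproducing the plan: 217/293 = 74.06%, which agrees with the stated 74%.
- No result: 293 − 217 = 76, and 76/293 = 25.9% (Wilson 95% CI 21.3% to 31.2%).
- Having a result is not the same as being positive, so 217 is an upper bound on documented positives.
- Phase 3 base: the count of 521 runs to 31 December 2020, but identification ends 31 August 2020. With even accrual from 01 June 2017, 521 × 1188/1310 days = 472. The base is therefore 472 to 521.
- At the same rate (assumption), documented positives number at most 472 × 0.7406 = 350 to 521 × 0.7406 = 386.

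**The case against.** **Table 1 governs.** The Abstract calls Table 1 the complete list of operational definitions, and Section 9.8.2 sends derivations there. That gives a reader some ground for preferring it. It does not settle the matter, because Section 9.3.3 is itself the sampling rule for Phase 2 charts and states the strict definition.

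**Mixed populations.** A reader might infer that Phase 2 charts followed one definition and Phase 3 charts will follow the other. The documents do not show this. Section 9.3.3 says that the Phase 1 and 2 stratifications will be replicated in Phase 3. What is shown is that the text permits either definition.

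**Old single tests.** A reader might infer that one ALK test at day −400 is missing under Section 9.3 but reported under the ALK row. That goes too far: the row's instruction applies only to multiple results, and its own period is Baseline. Nor do the documents show that the window would mainly affect non-front-line patients. Section 9.3 does allow fuller history for disease characteristics, with diagnosis and metastatic dates as examples, but it does not name biomarkers, and Table 1 lists them under Baseline.

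**ALK+ label.** Section 7 gives ALK+ metastatic NSCLC as the indication, so receipt is a reasonable proxy. Table 1 already has negative, not performed and not documented categories, and Section 9.8.3 reports categorical variables by cohort, so these counts will be visible. The 76 without a result are not shown to be ALK-negative. The 74% rate should not be carried to PFS: progression comes only from chart review, which also collects ALK status and supersedes structured data. All of this stands and makes the point minor.

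**Conclusion.** The point holds, with unequal weight across its parts.

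- **(a)** is a direct contradiction in a term that selects charts and defines outcome strata. It should be resolved before Phase 3 data are drawn. Its numerical effect cannot be derived from the documents.
- **(b)** is narrower. The explicit conflict concerns patients with more than one ALK result. The window problem covers ALK, histology and the other markers, rests on a literal reading of Baseline, and is most plausible in the lorlatinib cohort. Neither can be counted from the documents.
- **(c)** is a clarification. The plan states an assumption from ALK-inhibitor receipt for metastatic status (Table 1) but not for ALK positivity. About a quarter of feasibility patients had no result. That count covers treatment after 01 November 2017, so applying it to the full identification period is an assumption.

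**What to change.** **(a)** Reconcile the Abstract, Section 8, Section 9.3.3 and Table 1 to one front-line definition, and name it in Sections 9.2 and 9.3.4.2. Flag patients who qualify only through the 3-month exception, using chart notes where charts are reviewed, since Section 9.10.1 says that prior outside treatment is poorly captured. Report front-line outcomes with and without them. Phase 2 charts may need re-flagging.

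**(b)** In Table 1, set the period for the ALK, histology and other biomarker rows to all available history up to 30 days after index. Keep the 30-day window for time-varying items such as ECOG. State which of the two existing rules applies when there are several ALK results; a third rule is not needed. The cost is a wider query and aligned wording.

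**(c)** Add a sentence saying that alectinib receipt is the proxy for ALK positivity. Keep the full treated population as the main analysis. A sensitivity analysis of DOT and OS in documented-positive patients is optional. It would hold at most about 74% of patients, so confidence intervals would be at least about 16% wider (1/√0.7406 = 1.162) if events are spread evenly. In Phase 3 the group with subsequent therapy would fall from 94–156 (20% of 472 to 30% of 521) to at most 70–116 before the split into cohorts C to E, so some cohorts may be too small to repeat.

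Eligibility does not change. Section 6 plans Phase 3 extraction for October 2021 and chart review from November 2021, both after the 31 August 2021 protocol date, so the changes can precede both.
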